6.6.3. Vital Signs

Vital signs including systolic and diastolic blood pressures (mmHg), and PR (bpm) will be descriptively summarized for actual values and change from baseline to post-baseline time-points. For the change values, participants with both values at baseline and each respective time-point for calculating the change will be included. Participants who have both baseline and at least one post-baseline will be included in this summary.

Respiratory rate and temperature data collected during the study will be considered source data and will not be reported.

6.6.4. Electrocardiograms

The ECG parameters (Heart Rate, PR interval, QRS interval, QT interval, QTc interval) will be summarized for actual values and change from baseline at baseline and/or post-baseline time-points. The number and percentage of participants who have treatment emergent changes toward worst category in the ECG interpretations assessed by investigators will be summarized. The interpretations are the followings: Normal, Abnormal-Clinically Significant and Abnormal-Clinically Not Significant. Participants with ECG findings meeting the Protocol Appendix 7 criteria will be summarized.

QTc corrected using Fridericia's formula (QTcF) will be programmatically derived from QT and HR (ie. ECG Mean Heart Rate) using the following formula:

$$QTcF(msec) = QT(msec) / \sqrt[3]{(60/EGHRMN(beats/min))}$$

The number and percentage of participants with QTcF meeting the criteria in the following table will be summarized by treatment group in 2 ways: by taking all post-baseline values, and at EOT.

Type of Analysis	Criteria
Change from Baseline	Increase > 30 msec, Increase > 60 msec, Decrease > 30 msec, Decrease > 60 msec
Actual Values	< 300 msec, < 330 msec, < 360 msec, > 450 msec, > 480 msec, > 500 msec

A participant may be counted more than once in some categories above as they are not mutually exclusive.

6.6.5. Eye Examination

The eye examination records will be listed.

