
 To observe the additional safety and tolerability profile of isavuconazole. 	Other secondary safety endpoints: 
 Other AE summaries, including TEAE related to study intervention, Treatment-Emergent SAEs, TEAE leading to discontinuation of study intervention, TEAE leading to deaths, and all deaths. Other safety variables, including clinical laboratory variables, vital signs, 12-lead ECG and eye examination. 	
 Not applicable Not applicable

Objectives	Endpoints	Estimands

 To evaluate the PK of isavuconazole in the Chinese population with IFD caused by Aspergillus species and other filamentous fungi. 	
 Isavuconazole plasma concentrations at Day 3, 7, 14 and EOT visit. 	
 Not applicable
Exploratory	Exploratory	Exploratory

 To describe the efficacy of isavuconazole in the treatment of Chinese participants with IM. 	
 The percentage of all-cause mortality on Day 42 and 84 following primary treatment with isavuconazole. The crude rate of overall response at EOT, Day 42, and 84; and the crude success rates of the clinical, mycological, radiological responses based on the investigators' assessment at EOT, Day 42, and 84. 	
 The percentage of all-cause mortality on Day 42 and 84 will be estimated in participants with IM without regard to adherence to the isavuconazole treatment. The crude rate of overall response, clinical response, mycological response and radiological response at EOT, Day 42, and Day 84 will be estimated in participants with IM while participants are on the isavuconazole treatment. Data collected after use of the prohibited medications will not be used. Participants who are not available for clinical, mycological or radiological responses will be considered as a failure for overall response.
CCI		

If the investigator judges an SAE to have a causal relationship with the IMP, the investigator must additionally report the event to Pfizer Safety as described in [Section 10.3.3](#), Adverse Event Reporting section, even if that event is a component of the endpoint.

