9.3.2. Safety Analyses

Safety variables will be summarized descriptively for the safety population. 95% CIs for the binary outcome of selected safety variables may be presented based on an exact binomial distribution.

The primary safety endpoint is the incidence rates of TEAEs by SOC and PT. A TEAE is defined as any AE that starts on or after the first administration of study intervention until 28 days after last dose of study intervention. Other key summaries of AEs include the summaries of

- TEAE related to study intervention
- Treatment-Emergent SAEs
- TEAE leading to discontinuation of study intervention
- TEAE leading to deaths
- All deaths

Vital signs will be listed and summarized by means and standard deviation (SD). Laboratory test values will be presented in change from baseline and shift tables and by individual listings with flagging of values outside the normal reference ranges. ECG findings will be presented by listings and frequency tables, as appropriate.

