2.1. Modifications to the Analysis Plan Described in the Protocol

Not applicable (NA).

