3.2. Secondary Endpoint(s)

The key secondary endpoint is percentage of all-cause mortality on Day 42 following primary treatment with isavuconazole in participants with IFD.

The other secondary endpoints are for participants with IFD include:

- The percentage of all-cause mortality on Day 84 following primary treatment with isavuconazole.
- The crude rate of overall response based on the investigators' assessment at EOT, Day 42, and 84.
- The crude success rates of the clinical, mycological, radiological responses based on the investigators' assessment at EOT, Day 42 and Day 84.
- Other AE summaries, including TEAE related to study intervention, Treatment-Emergent serious adverse events (SAE), TEAE leading to discontinuation of study intervention, TEAE leading to deaths, and all Deaths.
- Other safety variables including clinical laboratory variables, vital signs, 12-lead ECG and eye examination.
- Isavuconazole plasma concentrations at Day 3, 7, 14 and EOT visit.

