3.5.1. Adverse Events

An AE is referred to TEAE in this study unless mentioned otherwise. See Section 3.1 for the definition of TEAE.

An abnormality identified during a medical test (e.g., laboratory parameter, vital sign, ECG data, physical exam) should be defined as an AE only if the abnormality meets one of the following criteria:

- Induces clinical signs or symptoms
- Requires active intervention
- Requires interruption or discontinuation of study medication

The abnormality or investigational value is clinically significant in the opinion of the investigator.

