5.2. General Methods

5.2.1. Analyses for Binary and Categorical Endpoints

Binary and categorical data will be summarized by number and percentage of participants within the category.

For all-cause mortality and crude rate, the 95% CIs for the rates will be calculated based on the exact binomial distribution.

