6.6. Safety Summaries and Analyses

- Analysis set: Safety population (Section 4).
- Analysis methodology: Different analysis methods will be performed for the safety variables as follows, respectively.

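### Eye examination is a named secondary safety endpoint, but the SAP plans only a listing, so new or worsened findings that are not adverse events are never counted

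*SAP*

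**What the plan says.** The protocol's objectives table (section 3) lists among the secondary safety endpoints "Other safety variables, including clinical laboratory variables, vital signs, 12-lead ECG and eye examination". SAP 3.2 repeats the item as "Other safety variables including clinical laboratory variables, vital signs, 12-lead ECG and eye examination".

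On analysis, Protocol 9.3.2 opens with a general commitment: "Safety variables will be summarized descriptively for the safety population". It then names outputs for vital signs, laboratory tests and ECG, and none for eye examination. SAP 6.6 hands each variable to its own subsection: "Different analysis methods will be performed for the safety variables as follows, respectively". The whole of SAP 6.6.5 is "The eye examination records will be listed". SAP 2.1, the place for departures from the protocol's analysis plan, is marked as not applicable.

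The examination has three parts (visual acuity, confrontational visual fields, colour perception). It is done at Screening and EOT, and on Days 14, 28 and 42 for participants still on drug (SAP 3.5.5; Protocol 8.3.5 adds visits for participants with mucormycosis). Protocol 8.3.5 has abnormalities entered in the eCRF.

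**The concern.** A listing shows individual records. It does not report how many participants had an examination that became abnormal or got worse. The other three variables on the same endpoint line all get descriptive summaries (SAP 6.6.2 to 6.6.4), and laboratory tests and ECG also get counts of shifts or worsening. Eye examination is the only one left without a number.

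The TEAE tables cover part of this but not all. Under SAP 3.5.1 a test abnormality is an adverse event only if it produces signs or symptoms, needs intervention, interrupts or stops drug, or satisfies the last condition: "The abnormality or investigational value is clinically significant in the opinion of the investigator". A changed acuity, field or colour result that meets none of these is recorded and listed but not counted. If nothing is changed, the report will be silent on that part of a declared endpoint, and a reader would have to compare visits by hand.

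**Working it through.** **1. Is there a route to a count elsewhere in the plan?**

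| Possible route | What it provides | Does it count non-AE eye findings? |
|---|---|---|
| SAP 6.6.5 | Listing only | No |
| SAP 6.1 and 6.6.1, TEAE tables | n and % by SOC and PT | Only findings that meet an AE criterion |
| SAP 5.2.1, general convention: "Binary and categorical data will be summarized by number and percentage of participants within the category" | Generic rule; no eye category, denominator, shift or visit defined | Not in practice, since SAP 6.6 points to the specific method in 6.6.5 |
| Protocol 9.3.2 | General promise of a summary | No eye-specific output named |
| SAP Appendix 3, analysis windows | Laboratory tests, vital signs, ECG | No eye-examination window |

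No route yields the count.

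**2. How does the SAP treat comparable data?** For ECG, SAP 6.6.4 counts participants whose investigator interpretation moves toward a worse category, and one of those categories is abnormal but not clinically significant. Findings below the AE threshold are therefore tabulated for ECG. SAP 6.6.6.1 also summarizes reason for hospitalization, which is not a named endpoint.

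**3. Size of the denominator.** Protocol 9.5 expects about 66 treated participants. Its own figure reproduces: the probability of seeing at least one event of 3% incidence is 1 − 0.97^66 = 0.866, as stated. The missing table does not affect it.

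**4. What the table could show.** No rate for non-AE eye findings is given, so the counts below are illustrative. Intervals are exact (Clopper-Pearson). With zero events the upper limit is 1 − 0.025^(1/n).

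- One participant: 1/66 = 1.5% (95% CI 0.04% to 8.2%).
- None: 0/66 = 0%, upper limit 1 − 0.025^(1/66) = 5.4%.
- None, if only 50 had both a baseline and a post-baseline examination (50 is an assumption): upper limit 1 − 0.025^(1/50) = 7.1%.

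**5. Context only.** Protocol 2.2.4 reports eye-disorder TEAEs in 15% of isavuconazole participants in the earlier phase 3 aspergillosis trial. At that rate 0.15 × 66 = 9.9, about 10 participants (10/66 = 15.2%, 95% CI 7.5% to 26.1%). Those would already be in the TEAE tables and are not the uncounted part.

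**The case against.** The best defence is that this is a choice of format. The endpoint line has no estimand, neither document defines an eye-examination event or shift, and the objective here is only to observe further safety. Protocol section 9 lets the SAP modify the protocol's outline, and requires an amendment only for major changes to the primary endpoint or its analysis. Findings of clinical consequence are already counted as TEAEs, so what remains is by construction asymptomatic, untreated and judged not clinically significant. QT shortening is a listed risk of the drug and eye toxicity is not, so lighter eye reporting than ECG reporting could be proportionate. SAP 5.2.1 might also be read as still applying. Finally, the eCRF is not among the documents, so coding by component or of worsening is unproven.

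Much of this stands as a limit on importance. It does not close the gap. If the SAP uses its freedom to replace a summary with a listing, SAP 2.1 should record that rather than report no modification. Reading SAP 5.2.1 as still in force leaves 6.6.5 ambiguous, which also calls for a wording change. The feasibility point is fair, and the proposed table has to allow for it.

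**Conclusion.** The concern holds, at minor severity. A declared secondary safety endpoint has only a listing. New or worsened eye-examination findings that meet no AE criterion would get no number or percentage, and the SAP does not declare this as a departure from the protocol.

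The number of participants affected cannot be estimated from the documents and may be zero. The conclusion rests on reading the specific sentence in SAP 6.6.5 as overriding the general rule in 5.2.1, which is the natural reading of SAP 6.6 but not the only possible one. The primary endpoint, the efficacy analyses and the sample size are unaffected.

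**What to change.** In SAP 6.6.5 keep the listing and add one table for the Safety population: number and percentage of participants with any new or worsened eye-examination abnormality, (a) at any post-baseline examination and (b) at EOT. The denominator is participants with a baseline and at least one post-baseline examination, with baseline as defined in SAP 3.4. Split by acuity, visual field and colour perception, with a baseline-by-worst shift, only if the eCRF codes status by component. If worsening is not coded, count new abnormalities only.

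If a listing alone is intended, state that in SAP 2.1 with the reason. SAP 6.6.3 sets a precedent by saying openly that respiratory rate and temperature will not be reported.

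The cost is SAP wording and one table, with no new visits or data. A participant-level count should be feasible, because abnormalities already go into the eCRF and sites must judge the EOT examination abnormal or not to decide whether to repeat it at Follow-up (SAP 3.5.5).

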6.6.6. Other Assessment

The summaries will be performed for safety populations.

6.6.6.1. Hospitalization Status

Reason for hospitalization from screening up through the 4 weeks post-treatment period will be summarized.

7. INTERIM ANALYSES

7.1. Introduction

An interim analysis will be performed to assess safety and efficacy after around 40% of the planned participants, i.e., approximately 28 participants, complete or have sufficient time to complete their study participation. The analysis methods in the interim report will follow the methods planned for the full study and will be based on communication with China agency.

7.2. Interim Analyses and Summaries

For development of the interim analysis report, the study database will be cleaned and a snapshot of the database will be created. As this is a single arm study and blinding is NA, final tables, figures and listings (TLFs), and interim report will be produced using snapshot data by study statistician and programmers.

Considering the small number of participants included in the interim analysis and availability of data, in addition to the general analyses planned in the above sections, more specifications are described below.

For the efficacy endpoints, only all-cause mortality rate on Day 42 and/or 84 will be analyzed including main analysis, supplementary analysis and subgroup analysis.

8. REFERENCES

None.

9. APPENDICES

Appendix 1. Summary of Efficacy Analyses

Endpoint	Analysis Type	Population	Data Inclusion and Rules for Handling Intercurrent Events and Missing Data	Analysis Model
The percentage of all-cause mortality on Day 42 following primary treatment with isavuconazole. (Key secondary endpoint)	Main analysis for the key secondary endpoints	ITT	All data collected (after prohibited medication or after discontinuation of treatment) will be included. See Section 5.3 for missing data handling method.	Crude rate, binomial distribution for CI.
	Sensitivity analysis	ITT	All data collected (after prohibited medication or after discontinuation of treatment) will be included. See Section 5.3 for missing data handling method.	Kaplan-Meier
	Supplementary analysis	mITT and myITT-IA	All data collected (after prohibited medication or after discontinuation of treatment) will be included. See Section 5.3 for missing data handling method.	Crude rate, binomial distribution for CI.
	Supplementary analysis	mITT, and myITT-IA	See Section 5.3 for missing data handling method.	Kaplan-Meier
	Subgroup analysis if data permit	ITT	All data collected (after prohibited medication or after discontinuation of treatment) will be included. See	Crude rate, binomial distribution for CI.

Endpoint	Analysis Type	Population	Data Inclusion and Rules for Handling Intercurrent Events and Missing Data	Analysis Model
			Section 5.3 for missing data handling method.	
The percentage of all-cause mortality on Day 84 following primary treatment with isavuconazole. (Secondary endpoint)	Secondary analysis	ITT	All data collected (after prohibited medication or after discontinuation of treatment) will be included. See Section 5.3 for missing data handling method.	Crude rate, binomial distribution for CI.
	Sensitivity analysis	ITT	All data collected (after prohibited medication or after discontinuation of treatment) will be included. See Section 5.3 for missing data handling method.	Kaplan-Meier
	Supplementary analysis	mITT and myITT-IA	All data collected (after prohibited medication or after discontinuation of treatment) will be included. See Section 5.3 for missing data handling method.	Crude rate, binomial distribution for CI.
	Supplementary analysis	mITT, and myITT-IA	See Section 5.3 for missing data handling method.	Kaplan-Meier
	Subgroup analysis if data permit	ITT	All data collected (after prohibited medication or after discontinuation of treatment) will be included. See	Crude rate, binomial distribution for CI.

Endpoint	Analysis Type	Population	Data Inclusion and Rules for Handling Intercurrent Events and Missing Data	Analysis Model
			Section 5.3 for missing data handling method.	
The crude rate of overall response based on the investigators' assessment at EOT. (Secondary endpoint)	Secondary analysis	mITT and myITT-IA	All data collected after use of the prohibited medications will be excluded.	Crude rate, binomial distribution for CI
	Subgroup analysis if data permit	mITT	All data collected after use of the prohibited medications will be excluded.	Crude rate, binomial distribution for CI
The crude rate of overall response based on the investigators' assessment at Day 42, and 84. (Secondary endpoint)	Secondary analysis	mITT and myITT-IA	All data collected after use of the prohibited medications will be excluded. Refer to Section 5.3 for handling missing data.	Crude rate, binomial distribution for CI
The crude success rates of the clinical, mycological, radiological responses based on the investigators' assessment at EOT, Day 42	Secondary analysis	mITT and myITT-IA	All data collected after use of the prohibited medications will be excluded.	Crude rate, binomial distribution for CI

Endpoint	Analysis Type	Population	Data Inclusion and Rules for Handling Intercurrent Events and Missing Data	Analysis Model
and Day 84. (Secondary endpoint)				
The percentage of all-cause mortality on Day 42 and Day 84 following primary treatment with isavuconazole. (Exploratory endpoint)	Exploratory analysis	myITT-IM	All data collected (after prohibited medication or after discontinuation of treatment) will be included. See Section 5.3 for missing data handling method.	Crude rate, binomial distribution for CI.
	Supplementary analysis	myITT-IM	See Section 5.3 for missing data handling method.	Kaplan-Meier
The crude rate of overall response based on the investigators' assessment at EOT, Day 42, and 84. (Exploratory endpoint)	Exploratory analysis	myITT-IM	All data collected after use of the prohibited medications will be excluded. Refer to Section 5.3 for handling missing data.	Crude rate, binomial distribution for CI.
The crude success rates of the clinical, mycological, radiological responses based on the investigators' assessment at EOT, Day 42 and Day 84. (Exploratory endpoint)	Exploratory analysis	myITT-IM	All data collected after use of the prohibited medications will be excluded.	Crude rate, binomial distribution for CI.

Appendix 2. Formulae for eGFR-CKD-EPI

The calculated glomerular filtration rate (GFR) will be estimated by CKD-EPI equations. Scr is baseline creatinine.

2021 CKD-EPI Scr Only	Scr (mg/dL)	Scys (mg/L)	Recommended eGFR Equation
Female	if ≤ 0.7	N/A	$eGFR = 143 \times (Scr/0.7)^{-0.241} \times (0.9938)^{Age}$
Female	if > 0.7	N/A	$eGFR = 143 \times (Scr/0.7)^{-1.200} \times (0.9938)^{Age}$
Male	if ≤ 0.9	N/A	$eGFR = 142 \times (Scr/0.9)^{-0.302} \times (0.9938)^{Age}$
Male	if > 0.9	N/A	$eGFR = 142 \times (Scr/0.9)^{-1.200} \times (0.9938)^{Age}$

Inker LA et al. N Engl J Med. 2021;385:1737-49.

If Scr increase is confirmed after baseline, then reflex measurement of Scys is indicated to estimate the combined Scr-Scys eGFR calculation (for adults only). Scys is CystatinC at baseline.

2021 CKD-EPI Scr-Scys Combined	Scr (mg/dL)	Scys (mg/L)	Recommended eGFR Equation
Female	if ≤ 0.7	if ≤ 0.8	$eGFR = 130 \times (Scr/0.7)^{-0.219} \times (Scys/0.8)^{-0.323} \times (0.9961)^{Age}$
Female	if ≤ 0.7	if > 0.8	$eGFR = 130 \times (Scr/0.7)^{-0.219} \times (Scys/0.8)^{-0.778} \times (0.9961)^{Age}$
Female	if > 0.7	if ≤ 0.8	$eGFR = 130 \times (Scr/0.7)^{-0.544} \times (Scys/0.8)^{-0.323} \times (0.9961)^{Age}$
Female	if > 0.7	if > 0.8	$eGFR = 130 \times (Scr/0.7)^{-0.544} \times (Scys/0.8)^{-0.778} \times (0.9961)^{Age}$
Male	if ≤ 0.9	if ≤ 0.8	$eGFR = 135 \times (Scr/0.9)^{-0.144} \times (Scys/0.8)^{-0.323} \times (0.9961)^{Age}$
Male	if ≤ 0.9	if > 0.8	$eGFR = 135 \times (Scr/0.9)^{-0.144} \times (Scys/0.8)^{-0.778} \times (0.9961)^{Age}$
Male	if > 0.9	if ≤ 0.8	$eGFR = 135 \times (Scr/0.9)^{-0.544} \times (Scys/0.8)^{-0.323} \times (0.9961)^{Age}$
Male	if > 0.9	if > 0.8	$eGFR = 135 \times (Scr/0.9)^{-0.544} \times (Scys/0.8)^{-0.778} \times (0.9961)^{Age}$

Inker LA et al. N Engl J Med. 2021;385:1737-49.

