10.6. Appendix 6: Kidney Safety Monitoring Guidelines

10.6.1. Laboratory Assessment of Change in Kidney Function and Detection of Kidney Injury

Standard kidney safety monitoring requires assessment of baseline and postbaseline serum creatinine (Scr measurement to eGFR [Scr-based eGFR] or [eCrCl]). Baseline and postbaseline Scys makes it feasible to distinguish AKI from other causes of Scr increase. If Scr increase is confirmed after baseline, then reflex measurement of Scys is indicated to estimate the combined Scr-Scys eGFR calculation (for adults only).

Regardless of whether kidney function monitoring tests are required as a routine safety monitoring procedure in the study, if the investigator or sponsor deems it necessary to further assess kidney safety and quantify kidney function, then these test results should be managed and followed per standard of care.

10.6.2. Age-Specific Kidney Function Calculation Recommendations:

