1. VERSION HISTORY

Table 1. Summary of Changes

Version/ Date	Associated Protocol Amendment	Rationale	Specific Changes
1 24 Jun 2022	Original 25 Apr 2022	N/A	N/A
2 12 March 2024	Amendment 2 29 Jan 2024	Aligned with the changes from protocol amendment	
Updated estimand for primary objective in Section 2.2 and 2.2.1.
 
Added the following statements in Section 2.3
 
“All participants receiving study medication will have the visits performed as scheduled.”
 
“For all participants, the Follow-up visit will take place 4 weeks (± 7 days) after the last administration of the study medication, and may occur before or after Day 42 and/or Day 84 (or Day 180 for participants with IM).”
 
Updated sample size in Section 2.3 to accommodate the modification in protocol amendment 2.
 
Updated content in Section 2.3 to clarify the culture and histology/ cytology antigen testing are applicable for both Aspergillus species and Mucorales species.
 
Made the following changes in Section 3.4:
 
 Added ‘Race’, ‘Ethnicity’, ‘Country’; Updated from ‘eGFR-MDRD’ to ‘eGFR-CKD-EPI’; Added ‘Prior allogeneic HSCT/BMT: Yes/No’, ‘Solid organ transplant: Yes/No’, ‘Hematologic malignancy: Yes/No’, ‘Other malignancy: Yes/No’;

Table 1. Summary of Changes

Version/ Date	Associated Protocol Amendment	Rationale	Specific Changes
			
‘Chronic respiratory airway abnormality: Yes/No’;
 
 Added primary diagnosis type Moved primary underlying disease to a separate Section 6.5.2; 
CCI
 
 Clarified the rule of determination of baseline variables. 
Added timepoints of ‘Day 84, every 42 days after Day 42’ in Section 3.5.2-3.5.3.
 
Updated timepoints for ECG in Section 3.5.4.
 
Corrected a typo from ‘GMc’ To ‘GM’ in Section 4. Removed the wording about p-value from Section 5 as p-value is not applicable for the study.
 
Added details of CI calculation from KM approach and details to define censoring participants in Section 5.2.3.
 
Added estimand strategy and intercurrent event in Section 6.1.
 
Modified ‘supplementary analysi’ to ‘sensitivity analysis’ for using KM method for all-cause mortality at Day 42 using ITT in Section 6.2.1.2.
 
Updated from ‘eGFR-MDRD’ to ‘eGFR’ in Section 6.2.1.3 and Appendix 2;

Table 1. Summary of Changes

Version/ Date	Associated Protocol Amendment	Rationale	Specific Changes

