3.4. Baseline Variables

Baseline is defined as the last observation on or prior to the first administration of study medication, unless otherwise specified.

The baseline variables in the study contain demographic and other baseline characteristics as follows.

- Age, Gender, Race, Ethnicity, Country, Height, Weight, Body mass index (BMI)
- Age category 1: ≤ 45 , > 45 to ≤ 65 , > 65
- Age category 2: ≤ 65 , > 65 to ≤ 75 , > 75
- BMI: < 25 , ≥ 25 to < 30 , ≥ 30
- eGFR- CKD-EPI category: < 60 , ≥ 60
- Baseline Neutropenic Status: Yes/No
- Use of T-cell/B-cell immunosuppressant: Yes/No
- Use of Corticosteroids: Yes/No
- Prior allogeneic HSCT/BMT: Yes/No
- Solid organ transplant: Yes/No
- Hematologic malignancy: Yes/No
- Other malignancy: Yes/No
- Chronic respiratory airway abnormality: Yes/No
- Primary diagnosis type: IA, IM, other

Details of derivation for eGFR-CKD-EPI are included in Appendix 2.

Baseline Neutropenic Status will be defined as “Yes” for participants who had Absolute Neutrophil Count (ANC) $< 0.5 \times 10^9/L$ [$< 500/mm^3$] at baseline.

Use of T-cell/B-cell immunosuppressant and Use of Corticosteroids will be determined based on clinical review with the prior medication data collected via CRF.

Prior allogeneic HSCT/BMT, Solid organ transplant, Hematologic malignancy, Other malignancy, and Chronic respiratory airway abnormality will be determined based on clinical review with the medical history data collected via CRF.

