6.6.2. Laboratory Data

All clinical laboratory values including Hematology, Chemistry and Urinalysis from a local laboratory will be summarized. Laboratory values (actual values and change from baseline) will be descriptively summarized by visit. The change from baseline for urinalysis will include pH parameter. Number and percentage of participants with shifts from baseline to post-baseline will be summarized for the following:

- 1) An upward shift from baseline to post-baseline (i.e. L to N, L to H, or N to H)
- 2) No change from baseline to post-baseline (i.e. L to L, N to N, or H to H)
- 3) A downward shift from baseline to post-baseline (i.e. H to N, H to L, or N to L).

The individual listing of laboratory data will also be generated with flagging of values outside the normal reference ranges

In addition, potential hepatotoxicity and nephrotoxicity will be summarize.

Assessment of Hepatotoxicity

Potential hepatotoxicity will be summarized descriptively. The number and percentage of participants who meet the following criteria based on either local or central laboratories

including post-baseline data collected within post-dosing window will be summarized for the following criteria.

- Alanine aminotransferase (ALT) or Aspartate aminotransferase (AST) > 3xULN, > 5xULN, > 10xULN, >20xULN
- ALT > 3xULN, > 5xULN, > 10xULN, >20xULN
- AST > 3xULN, > 5xULN, > 10xULN, >20xULN
- Alkaline phosphatase (ALP) > 1.5xULN, >3xULN
- Total Bilirubin >2xULN
- ALT or AST > 3xULN and Total Bilirubin > 1.5xULN
- ALT or AST > 3xULN and Total Bilirubin > 2xULN
- ALT or AST > 3xULN and ALP < 2xULN and Total Bilirubin > 2xULN

A participant may be counted more than once as the categories are not mutually exclusive (ie., a participant with a value >10xULN will be counted in both 3xULN and 5xULN categories). The analysis will be conducted by taking all post-baseline values.

Assessment of Nephrotoxicity

Serum creatinine either from local or central lab will be further analyzed by the following 3 categories:

- $\geq 25\%$, $\geq 50\%$, $\geq 100\%$ increase from baseline.

The categories are not mutually exclusive, thus a participant may be counted in more than one category. Participants with both baseline and at least one post-baseline will be included in this summary. The number and percentage of participants meeting the defined criteria will be summarized by treatment group in 2 ways: by taking all post-baseline values, and at EOT

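### As written, SAP Appendix 2 lets a creatinine rise after dosing decide which equation sets the baseline eGFR category

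*SAP*

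**What the plan says.** SAP 3.4 gives the general rule: "Baseline is defined as the last observation on or prior to the first administration of study medication, unless otherwise specified". It lists the eGFR-CKD-EPI category, cut at 60, among the baseline variables and adds: "Details of derivation for eGFR-CKD-EPI are included in Appendix 2". The SAP version history ties the same derivation to the subgroup analysis, recording the change of eGFR formula "in Section 6.2.1.3 and Appendix 2".

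Appendix 2 then says three things that matter here:

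- On creatinine: "Scr is baseline creatinine". The creatinine-only equations follow, with no condition attached.
- On when the combined equations apply: "If Scr increase is confirmed after baseline, then reflex measurement of Scys is indicated to estimate the combined Scr-Scys eGFR calculation". No other condition for using them is given.
- On cystatin C: "Scys is CystatinC at baseline".

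The conditional sentence also stands in protocol 10.6.1, which is about kidney monitoring and begins: "Standard kidney safety monitoring requires assessment of baseline and postbaseline serum creatinine". There it governs when a reflex cystatin C sample is taken.

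**The concern.** A baseline subgroup should be fixed by what was known at first dose. Here both inputs are baseline values, but the only stated trigger for changing equation is an event after dosing. A programmer who follows Appendix 2 to the letter would classify most participants by creatinine alone and reclassify those whose creatinine later rose.

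Renal decline may go with a worse outcome, and a participant who dies early has less time to show a confirmed rise. Membership of the subgroup could therefore be related to the outcome being tabulated within it.

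The category is used in the baseline summaries (SAP 6.5.1), in the eGFR subgroups for Day 42 and Day 84 mortality in the ITT population (6.2.1.3, 6.2.2), in the subgroups for overall response at EOT in the mITT population (6.2.3.1.1), and in the interim mortality subgroups on about 28 participants (7.1, 7.2).

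**Working it through.** The plan states no figure to reproduce on this point. The check has three parts.

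**1. Does the combined equation have another use in the SAP?** The visible text shows none. The nephrotoxicity analysis in SAP 6.6.2 is based on creatinine, not eGFR: "Serum creatinine either from local or central lab will be further analyzed by the following 3 categories", namely rises of at least 25%, 50% and 100% from baseline. Protocol Table 7 requires cystatin C at baseline, so the literal rule could be carried out. Redacted SAP sections may use eGFR elsewhere.

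**2. Can the choice of equation move the same baseline sample across 60?** The Appendix 2 equations for creatinine (Scr, mg/dL) and cystatin C (Scys, mg/L) above their knots are:

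- Man, creatinine only: 142 × (Scr/0.9)^−1.200 × 0.9938^age
- Man, combined: 135 × (Scr/0.9)^−0.544 × (Scys/0.8)^−0.778 × 0.9961^age
- Woman, creatinine only: 143 × (Scr/0.7)^−1.200 × 0.9938^age
- Woman, combined: 130 × (Scr/0.7)^−0.544 × (Scys/0.8)^−0.778 × 0.9961^age

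The ages and laboratory values below are illustrative, not from the documents. For a man aged 60 with Scr 1.2 and Scys 1.4:

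- Creatinine only: 142 × 0.7081 × 0.6886 = 69.2
- Combined: 135 × 0.8551 × 0.6470 × 0.7910 = 59.1

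| Age 60 | Scr | Scys | Creatinine only | Combined | Change of category |
|---|---|---|---|---|---|
| Man | 1.2 | 1.4 | 69.2 | 59.1 | down to <60 |
| Man | 1.5 | 1.0 | 53.0 | 68.0 | up to ≥60 |
| Woman | 1.0 | 1.3 | 64.2 | 58.1 | down to <60 |
| Woman | 1.2 | 1.0 | 51.6 | 64.5 | up to ≥60 |

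The category can change in either direction.

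**3. How much could this move subgroup mortality?** The documents give no distribution of creatinine or cystatin C, so this is an illustration only. From the documents: 66 treated (protocol 9.5) and 19% Day 42 mortality (the isavuconazole ITT figure in protocol 2.2.4). That gives 0.19 × 66 = 12.54 deaths and 53.46 survivors. The following are assumed:

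- no true link between eGFR and death;
- p0 = 20% below 60 by creatinine only;
- p1 = 12% to 40% below 60 by the combined equation;
- a confirmed rise in rd = 30% to 50% of deaths and rs = 10% to 15% of survivors.

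The share below 60 is d = (1−rd)·p0 + rd·p1 among deaths and s = (1−rs)·p0 + rs·p1 among survivors. The <60 group has n = 12.54d + 53.46s. The shift in deaths is 12.54d − 0.19n.

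Worked case with p1 = 0.40, rd = 0.50, rs = 0.10: d = 0.30, s = 0.22, n = 3.76 + 11.76 = 15.5, and the shift is 3.76 − 0.19 × 15.52 = +0.81.

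| p1 | rd | rs | n below 60 | Shift in deaths |
|---|---|---|---|---|
| 0.12 | 0.50 | 0.10 | 12.3 | −0.33 |
| 0.12 | 0.30 | 0.15 | 12.3 | −0.12 |
| 0.30 | 0.30 | 0.15 | 14.4 | +0.15 |
| 0.35 | 0.50 | 0.15 | 15.3 | +0.53 |
| 0.40 | 0.50 | 0.10 | 15.5 | +0.81 |

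If p1 equals p0 the shift is zero. For scale, 3 deaths among 15 participants has an exact (Clopper-Pearson) 95% interval of 4.3% to 48.1%.

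**The case against.** The strongest reply is that the sentence tells someone to take a sample and does not classify anyone. It comes from the monitoring text in protocol 10.6.1, and nothing in the SAP says outright that a baseline category is to be re-derived. The baseline definition in 3.4 and the unconditional creatinine-only table are enough to classify everyone, and the sentence contradicts itself, because a reflex sample taken after a rise cannot be the baseline sample. Much of this stands: creatinine only is probably what was meant. It does not repair the text. Protocol 10.6.1 speaks of baseline and post-baseline cystatin C, whereas the SAP fixes cystatin C at baseline inside the appendix that derives the baseline variable.

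A second reply is that protocol 10.6.3 grades decline in kidney function by eGFR, which would give the combined equation a purpose after baseline. That grading does not call for baseline cystatin C and does not alter the SAP derivation.

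Three further points are fair:

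- The bound of less than one death holds only within the stated assumptions. Raising rd to 0.60 with p1 = 0.40 and rs = 0.10 gives +1.02; p1 = 0.50 with rd = 0.50 and rs = 0.10 gives +1.22.
- Using the combined equation for everyone would also be free of post-baseline information, since baseline cystatin C is required.
- The practical consequence is slight.

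**Conclusion.** The point holds, and it is minor. Taken as written, Appendix 2 makes a baseline category depend on a post-dose event, against the SAP's own definition of baseline. That the wording gives this result is clear; that anyone intended it is unlikely.

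The effect is confined to one row of the baseline table and to descriptive subgroups. SAP 5.1 plans no formal hypothesis test for efficacy, and the primary TEAE analysis and the overall mortality estimates are untouched. The true size and sign of any effect on subgroup mortality are unknown. On the assumptions above the shift runs from −0.33 to +0.81 deaths in a group of about 12 to 16, well inside the sampling uncertainty. The conclusion also assumes that no redacted SAP section gives the combined equation a separate role or states which equation sets the category.

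**What to change.** In SAP Appendix 2, state that the baseline eGFR category uses the creatinine-only equation with baseline creatinine for every participant. This matches the likely intent and the order of the appendix. Then either delete the conditional sentence, or confine it to post-baseline monitoring with creatinine and cystatin C from the same post-baseline sample and state that it has no effect on the baseline category.

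The cost is one or two sentences before database lock. It needs no new data, visits, tables or protocol amendment.
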